Each WLQ score indicates the mean percentage of time in the 2 weeks prior to baseline that health problems limited ability to perform each category of work tasks: time management, physical tasks, mental and interpersonal tasks and output tasks (related to quality, quantity and timeliness of work). For example, among employees with mild depression symptom severity, work limitation scores range from being limited 19% of the time to 28% of the time. For those with moderate symptom severity, the range is 20% of the time to 42% of the time. For employees with severe symptoms, limitations range in frequency from 32% of the time to 61% of the time. The associated at-work productivity loss was between 7 to 14% on average in the three respective severity groups. Mean absences due to health or medical care in the prior two weeks ranged from just under 1 day to 2.4 days. Missed days translate into productivity losses between 7% and 22%. The burden of depression is also reflected by diagnosis. Functioning is poorest in the double depression group. Finally, the number of co-morbid conditions, which in this study are primarily physical, was important only for performance of physical job tasks.

- I. Purpose of the Project: (Clearly provide the purpose of this research project.) This study's goal is to enable employed veterans with a depression disorder to remain functionally independent and participate fully in the labor market. Its Aim 1 objective is to test the effectiveness of an innovative telephonic counseling program for employed veterans with depression, the Veterans Work and Health Initiative (V-WHI), which uses both psychological and vocational interventions. The Aim 2 objective, which is contingent on the effectiveness of the V-WHI, is to quantify its return on investment (ROI). This study will have three sites: the Cpl. Michael J. Crescenz VAMC, theVA, and the VA TVHS. The Coatesville VAMC was closed as a study site in August 2016, and further references to the closed site no longer appear in the protocol summary.

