- J. Describe the Research Questions or Hypotheses (that is, what questions are you trying to address by conducting the research.) The effectiveness of the V-WHI approach will be tested in the context of a randomized controlled trial (RCT). The following hypothesis will be tested: veterans receiving V-WHI will have better work outcomes at time 1 (T1) than the usual care group (BHL only) as measured by at-work productivity loss known as presenteeism. A sub-hypothesis for Aim 1 is that the V-WHI effect at T1 will be sustained at least until the final follow-up (T2). Secondary T1 outcome measures expected to improve include absenteeism, depression symptoms and health-related quality of life (HRQOL). Hypothesis 2 is that the return on investment (ROI in the V-WHI at time T1 will be positive, exceeding 1). Analysis of ROI will be contingent upon confirmation of Hypothesis 1. ROI will be estimated based on the marginal group difference in productivity (presenteeism and absenteeism combined) relative to the marginal V-WHI program costs.
- K. Primary Outcome Variable(s): (Define the primary outcome variable(s) used to support the study objectives (e.g. if the objective is to show that treatment A is superior to treatment B in the treatment of subjects with essential hypertension, the primary outcome variable is blood pressure measurement.) The main variables for outcomes analysis quantify health-related decrements in work performance and productivity (presenteeism). In addition, we will assess work loss and work retention based on employment status and other work outcomes such as weekly hours. To help us interpret the scores, we have extensive comparative data from clinic and population-based samples for the Work Limitations Questionnaire (WLQ), the WLQ Time Loss Absence Module,(11;12) and other employment status items (e.g., job loss).

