### Aim 1. Secondary Analyses

In this section we discuss: 1) analysis of secondary outcomes, 2) analysis of T2 outcomes, and 3) sensitivity testing of outcomes (other than the primary outcome) These include: absenteeism (time missed and productivity loss – the ratio of time missed to time expected to work), combined productivity loss due to presenteeism and absenteeism, unemployment at follow-up, job turnover, individual WLQ scale scores, the PHQ-9 severity score, and the VR-12 PCS and MCS. These are considered secondary outcomes. The impact of the V-WHI on the secondary outcomes will be tested using ANCOVA models similar to those mentioned in the discussion of the study's Hypothesis 1 analysis.

Testing for T2 outcomes (instead of T1) will determine if the intervention effects observed at T1 are maintained. These analyses will use ANCOVA models similar to those described above and applied to all outcomes.

For the additional sensitivity analyses, the methods will be similar to those described for the hypothesis 1 study endpoint. In addition, we will conduct additional analyses to address some specific issues not addressed in relation to the primary study endpoint. For example, regarding productivity loss due to absences (time missed/time expected to work), previous studies suggest that the distribution of the data is heavily skewed to the right, i.e., more people are centered around average of 10% and a few people tend to have rather large values towards 100%. In regard to that, we will specify transformations of the absenteeism data to reduce the undue influence of long right tails. Another example pertains to self-report. Because key primary and secondary outcomes will be assessed from questionnaires, and the treatment cannot be effectively blinded, we will test for self-report bias. For this purpose, we can look at job loss during the post-baseline period. Job loss is a good candidate for this test because it is not an evaluative variable, but an event report. While job losses are expected to occur relatively infrequently in the study time period, we may have enough cases by final follow-up to conduct this analysis. The strong relationship between self-reported functioning, PHQ-9, and WLQ outcomes at T1 and loss of job at T2 should be equally strong in both the treatment and control groups. If treatment subjects who lose their jobs have lower WLQ and PHQ-9 scores at T1 then we would suspect that the reported scores at T1 are too low.

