Benefits: We will compute benefits by quantifying and monetizing two components of productivity loss: presenteeism and absenteeism. For each component, we will compare the average change in the usual care and V-WHI care groups. We estimate productivity losses due to presenteeism using a validated WLQ Productivity Loss algorithm. Absenteeism is computed as hours of missed work during the time period divided by hours usually worked during that time period. Each productivity loss component will be monetized by multiplying it by the sample's median (fully loaded) wage. We use the median wage because we expect the wage distribution to be right skewed, making the mean less representative of the typical worker.

The benefit (i.e., reduced productivity loss) for the V-WHI intervention can be computed as follows. Let  $\triangle AP$  be the reduction in the proportion of time absent for V-WHI compared to usual care, while  $\triangle PP$  is the corresponding reduction in productivity loss due to presenteeism (i.e., the reduction in the proportion of output lost to presenteeism while working). Let H be the number of work hours during the period, while W is the median fully loaded wage rate. Then saved hours of productive output for V-WHI is H x ( $\triangle AP+\Delta PP$ ). Multiplying this result by W yields the monetized value of the reduced productivity loss.

Costs: The intervention's incremental cost has three components: 1) The value of time counselors spend in training is the product of their (fully loaded) wage rate and the number of hours needed to complete training; 2) The incremental value of time counselors spend counseling is the product of their fully loaded wage rate and the additional hours they spend counseling (compared to usual care); 3) The incremental value of time patients spend being counseled is the product of their fully loaded wage rate (the median veteran wage) and the additional hours they spend in counseling (compared to usual care).

The most straightforward cost and benefit analysis would compare the value of the benefit (i.e., the value of the reduced productivity loss) to the incremental cost of counseling. Because of the project's scale, changes in benefits will then be compared with changes in incremental costs.

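### The ROI benefit formula applies one undefined H to absenteeism and presenteeism reductions that have different bases, so overlapping losses are counted twice if H means usual hours

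*Combined protocol and SAP*

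**What the plan says.** The rule is in section W.4.2 of the combined protocol and SAP, under Hypothesis 2, Benefits.

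- Absenteeism: "Absenteeism is computed as hours of missed work during the time period divided by hours usually worked during that time period". Its change, ΔAP, is said to "be the reduction in the proportion of time absent for V-WHI compared to usual care".
- Presenteeism and H: ΔPP is "the reduction in the proportion of output lost to presenteeism while working). Let H be the number of work hours during the period". Section J describes the same presenteeism quantity in Hypothesis 1: "as measured by at-work productivity loss known as presenteeism".
- Combination: "Then saved hours of productive output for V-WHI is H x" (ΔAP + ΔPP). The result is multiplied by the median fully loaded wage W.
- H is called only the work hours in the period. The text does not say whether these are usual hours or hours attended.

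Under Aim 1, Secondary Analyses, the plan also lists "combined productivity loss due to presenteeism and absenteeism" as a secondary outcome and gives no formula for it.

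**The concern.** The two proportions have different denominators. Absenteeism is a share of all the hours a veteran would usually work. Presenteeism is a share of output in the hours actually attended. Multiplying both by usual hours credits presenteeism savings to hours nobody worked, and credits a recovered absent hour with full output although it still carries presenteeism loss. Multiplying both by attended hours makes the presenteeism term right but puts the absence term on too small a base. No reading of H makes both terms exact.

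At stake is the numerator of Hypothesis 2, which compares the ROI with a threshold of 1. The section on power says that the planned 1.2-point presenteeism effect is worth about as much as the maximum expected cost of treatment. The design therefore sits near break-even, where a proportional error in the benefit can change the conclusion.

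**Working it through.** **The plan's own figure.** The plan states no benefit or ROI value, so there is none to reproduce. The nearest figure is 83% power for a 1.2-point presenteeism reduction with 100 per arm. No SD is given, so it can only be solved backwards: a two-sided 5% test implies a residual SD of about 2.91 points. Nothing below depends on it.

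**Inputs.**
- Absence level A: 7% to 22% (section H, Preliminary Studies); centred near 10% (Aim 1, Secondary Analyses).
- Presenteeism level P: 7% to 14% (Preliminary Studies); 9% to 10% in employed veterans (Background), taken as 9.5%.
- Presenteeism reduction dP: 1.2 points (Power Analysis and Sample Size).
- Absence reduction dA: not given; assumed to be 0, 1.2 or 3 points.

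**Formula.** On the plan's definitions, output per usual hour is (1 - A)(1 - P), so combined loss is L = A + (1 - A) x P = A + P - AP. Write U for usual care and V for V-WHI, with A_V = A_U - dA and P_V = P_U - dP. Then:

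L_U - L_V = dA + dP - (A_U x dP + P_V x dA)

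The plan's sum, dA + dP, is too large by A_U x dP + P_V x dA when H is usual hours.

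**H as usual hours, central case** (A 10%, P 9.5%, dA = dP = 1.2 points):
- Plan: 0.012 + 0.012 = 0.0240, or 24.0 hours per 1,000 usual hours.
- Excess: 0.10 x 0.012 + 0.083 x 0.012 = 0.0012 + 0.000996 = 0.002196.
- Without overlap: 0.0240 - 0.002196 = 0.0218, or 21.8 hours.
- Overstatement: 0.002196 / 0.021804 = 10.1%.

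| A, P in usual care | dA = 0 | dA = 1.2 | dA = 3 |
|---|---|---|---|
| 7%, 7% | 7.5% | 6.8% | 6.5% |
| 10%, 9.5% | 11.1% | 10.1% | 9.6% |
| 22%, 14% | 28.2% | 21.1% | 18.2% |

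Other pairings of these levels stay within 6.5% to 28.2%. With dA = 0 the overstatement is 1/(1 - A) - 1.

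**Effect near the threshold.** With dA = 1.2 points, a benefit-to-cost ratio of 1.00 by the plan's formula becomes 0.91 in the central case (0.021804 / 0.024), 0.94 at 7%/7% and 0.83 at 22%/14%. If the 1.2-point break-even was valued over all usual hours (an assumption), it becomes 1.2/(1 - A) with no absence gain: 1.29, 1.33 and 1.54 points at A = 7%, 10% and 22%.

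**H as attended hours.** The plan's sum is scaled by 1 - A_U or 1 - A_V, depending on whose attendance is used.
- Central case: 0.90 x 0.024 = 0.0216 (-0.9%) or 0.912 x 0.024 = 0.0219 (+0.4%), against 0.0218.
- Lowest: A 22%, P 7%, dA 3 points, usual-care attendance: 0.78 x 0.042 = 0.0328 against 0.0376 (-12.9%).
- Highest: A 7%, P 14%, dA 3 points, V-WHI attendance: 0.96 x 0.042 = 0.0403 against 0.0373 (+8.0%).
- With dA = 0 there is no error.

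**The case against.** The strongest reply is that H is undefined and that the plan uses a different phrase for it than for the absenteeism denominator. If H means attended hours, the error is negligible centrally and can run against V-WHI. That stands: a reader might infer that the formula always inflates the benefit, and the documents do not support this. Usual hours is still the more natural reading, because H x ΔAP equals absent hours saved only on that base. Either way, H has to be defined.

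A reader might also infer that the combined secondary outcome has the same flaw and could exceed 100% for a veteran with near-total absence. The documents do not support that either. The secondary-outcomes text states no combination rule, and the ROI rule adds between-group reductions, not one person's levels. What can be said is that the outcome lacks a definition.

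The size also needs care. The 28% figure needs 22% absence, the top of a range from an employer-based trial in middle-aged and older workers, and no absence gain. The exact excess depends on T1 levels in this trial, which the documents cannot give. The dA values are assumptions.

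Finally, the analysis is run only if Hypothesis 1 is confirmed. This limits the consequence, but it also means that dP is positive whenever the formula is used. In the central case with H as usual hours, the excess changes sign only if absence worsens by more than about 1.4 points (0.10 x 1.2 / 0.083), where the additive benefit is itself negative.

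**Conclusion.** The structural error holds: the formula uses one base for two proportions that need different ones and has no term for the overlap. That the benefit is overstated is conditional on H meaning usual hours. On that reading, the best single figure is about 10% to 11% at 10% absence and 9.5% presenteeism, with 6.5% to 28% as the range over the documents' levels. On the attended-hours reading, the error has no fixed direction.

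These figures rest on dP = 1.2 points, an assumed dA of 0 to 3 points, levels borrowed from other samples, and products of group means. If absence and presenteeism are positively correlated across veterans, the overlap in levels is larger than those products show. The point bears on Hypothesis 2 when the ROI is near its threshold. It does not touch the primary test. The plan's ROI expression, written as cost minus benefit over cost, is a separate matter that correcting this numerator would not resolve.

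**What to change.** In the Benefits text:

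1. Define H as usual (expected) work hours in the period.
2. Compute each veteran's combined loss L = A + (1 - A) x P at baseline and at T1, with A and P as proportions.
3. Set the benefit to H x W x D, where D is the average fall in L from baseline to T1 under V-WHI minus the average fall under usual care (or the baseline-adjusted difference).

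Working per person keeps the plan's comparison of average change and carries the correlation between absence and presenteeism. Inserting group mean levels at T1 into a product would do neither.

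Under Aim 1, Secondary Analyses, define the combined outcome by the same L, so that it agrees with the ROI numerator and lies between 0 and 100%.

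The cost is a few lines of text. Table 1 already schedules the WLQ and its Time Loss Module at baseline and T1, so no new data are needed. If the plan meant usual hours, the estimated benefit would typically fall by roughly a tenth.

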### VINCI: Data Collection

VA provides care to Veterans at over 1,400 points of care. At the core of virtually all care processes is a broadly scoped and extensively used electronic health record system known as the Veterans Information System Technology Architecture (VistA). VistA provides a longitudinal view for patients receiving care nationwide including diagnoses, procedures, medications, labs, physiologic measurements, and text notes and reports. VA uses 130 VistA implementations to provide electronic health record services nationwide for just over 20 million Veterans historically. The aggregate content of these 130 VistA systems includes 2.3 billion documents (e.g., Progress Notes, Discharge Summaries, Reports) accumulating at a rate of 696,000 each day; 6.2 billion lab values (+1.5 million each day), 3.4 billion orders (+845,000 each day), and 1.7 billion medication administrations and prescription fills (+390,000 each day).

Data are aggregated from individual VistA systems to the VA Corporate Data Warehouse where it is modeled and prepared for use. Data published by the VHA Decision Support System (DSS), Inpatient and Outpatient Medical SAS (MedSAS), VA Health Economics Resource Center (HERC) cost data, Vital Status and VA-CMS linked data files maintained by VA Information Resource Center (VIReC), CDC National Death Index VA-linked data, and several other specialty data sets can be requested through VINCI. VA National Data Services and other data stewards regulate the right to use the data, but VINCI facilitates the process. When study requests are approved, project-specific data are extracted from source databases and placed in SQL tables accessible only to the research team and VINCI data managers.

### Storage of Study Data

Study data will be kept in accordance with the Department of Veterans Affairs Record Control Schedule 10-1 (RCS 10-1). Storage and transfer of any Personally Identifiable Information (PII) or Protected Health Information (PHI) must be done in accordance with applicable VA and VHA policies and directives, state and federal regulations, and applicable statutes including the Health Insurance Portability and Accountability ACT (HIPAA). Unless explicitly requested and approved by data stewards, all sensitive patient data must remain on VINCI project servers and only aggregate data without PII / PHI may be transferred from VINCI. Any desired change in data storage location or transfer requires amending the original data request with an updated of disposition of study data. The amendment must be approved by all data stewards before data may be transferred.

Violations of data policy or approved use of data will be subject to full penalty of law, which may include suspension of access privileges, reprimand, suspension from work, demotion, removal, and criminal and civil penalties.

Upon completion of the research project, the study principal investigator in conjunction with the VA Information Security Officer (ISO), and in accordance with VA policy, will ensure that, study data containing R&D Service (151)

sensitive, confidential information will be returned to the VA, sanitized and removed from all servers, desktops, removable storage devices, etc.

Data Access

Only study team personnel explicitly authorized by data stewards will have access to project data. The study principal investigator has the responsibility for security of study. VINCI data managers and VA OI&T personnel not under the purview of the study principal investigator control the servers, network, processors, firewall and software in the VINCI environment, including access rights granted to study personnel.

When study personnel are no longer part of the research team, the study principal investigator will amend the data access request to terminate that person's access to all study data and notify the VA Information Security Officer of such action. No sensitive patient data may be shared with anyone who does not have a VA appointment. All study team personnel with access to sensitive patient data must stay current on required VA information security and privacy policy trainings.

- 2.2.4. Provide a copy of the SOP. Attached in submission.
- 3. Will PHI be collected prior to obtaining informed consent? XYES NO N/A
  - 3.1.1. If yes, complete and provide a HIPAA Waiver of Individual Authorization for
    - Disclosure of Protected Health Information with this submission.
- 4. HIPAA Identifiers Indicate the PHI that will be collected from project participants directly or indirectly.
  - 4.1. 🛛 Name
  - 4.2. All geographic subdivisions smaller than a State, including street address, city, county, precinct, zip code, and their equivalent geocodes, except for the initial three digits of a zip code if, according to the current publicly available data from the Bureau of the Census
  - 4.3. All elements of dates (except year) for dates directly related to an individual, and all ages over 89 and all elements of dates (including year) indicative of such age, except that such ages and elements may be aggregated into a single category of age 90 or older.
    - 4.3.1. Birth Date
- Date of Death
- 4.3.2. Discharge date
- Admission date
- 4.3.3. Appointment Dates Other Dates (e.g. lab tests, x-rays, MRI, etc.)
- 4.4. X Telephone numbers
- 4.5. E Fax numbers
- 4.6. Electronic mail addresses
- 4.7. Social Security Number
- 4.9. Health plan beneficiary numbers
- 4.10. Account Numbers
- 4.11. Certificate/license numbers
- 4.12. Uvehicle identifiers and serial numbers, including license plate numbers
- 4.13. Device identifiers and serial numbers
- 4.14. UWeb universal resource locators (URLS)
- 4.15. Internet protocol (IP) address numbers
- 4.16. Biometric identifiers, including fingerprints, voiceprints, audio recordings
- 4.17. Event Full-face photographic images and any comparable images
- 4.18. Any other unique identifying number, characteristic, or code

Page 34 of 42

- 4.19. Personal and Family History
- 4.20. History and Physical Examination
- 4.21. Discharge Summary(ies)
- 4.22. 🗌 X-Ray
- 4.23. Diagnostic/Laboratory tests
- 4.24. Drug Abuse Information
- 4.25. Alcoholism or Alcohol Use
- 4.26. 
  Billing records
- 4.27. Health Summary Reports
- 4.28. Other Records:

- Progress Notes
- Photographs, videotapes, other images
- HIV (testing or infectious disease) records
- 🗌 Sickle cell anemia
- Behavioral Health notes
- Operative Reports
- Medication List
- Anatomic Pathology Report
- 5. Will participants be contacted from existing PHI? XYES NO N/A
  - 5.1. If yes, clearly explain how participants will be contacted (NOTE: this would be the same information as listed under section R.8 identification and recruitment of subjects). At the CMCVAMC, study staff will be given referrals from the BHL clinical staff. They will receive name, phone number and last 4 of SSN.
- 6. Provide the titles of the exact individuals who will have access to the collected data. Principal Investigator, Research Coordinator(s), Research Assistant(s), Statisticians, Investigators, study therapists/clinicians
  - 6.1. Explain why these individual will have access to this data. Necessary for participant contact, collected data, and data analysis
- Y. Information Security (Contact the Information Security Officer for additional assistance regarding confidentiality (storage/security) of research data.)
  - 1. Provide the precise plan how data is to be collected or acquired (repeat the same information as listed under "Data Collection" section of this form.

V-WHI clinical care is entirely telephonic and data will be entered into the counselor information system on a secure VA server. BHL usual care is telephonic and/or inperson. Study baseline, T1, and T2 follow-up questionnaires can take place in-person or over the telephone. Some data will be obtained from the electronic medical records and VINCI. Utilization of the V-WHI (visits, homework assignments completed) will be obtained from the V-WHI counselor information system. Collected data from the neuropsychological battery are uploaded automatically to the VA MIRECC secure server using PGP encryption and reviewed for validity.

The data analyses principally will use self-report data obtained from study questionnaires. Data from these sources will be supplemented with selected variables from the BHL clinical assessment (used for eligibility screening), VINCI, and VA electronic health record data. Study questionnaires will take approximately 45 minutes to complete. The main variables for outcomes analysis quantify health-related decrements in work performance and productivity. In addition, we will assess work loss and work retention based on employment status and other work outcomes such as weekly hours. Secondary outcome variables will include depression symptom severity and HRQOL. The former is measured with the PHQ-9. The latter is measured with the VR-12 which generates a physical component score (PCS) and a mental component score (MCS).

- 2. Provide a listing of the exact research data that will be stored, including but not limited to signed, original informed consent and HIPAA authorization forms, case report forms, etc. signed, original informed consent including the mini quiz and HIPAA authorization form, all assessments, data collected on the V-WHI intervention visits, and the computerized neuropsychological battery data.
- 3. Indicate how project's research data (original and all copies) will be stored and provide corresponding security systems. Any paper forms, including informed consent and HIPAA,

will be stored in locked cabinets in MIRECC Room B228. Clinical and research data will be stored electronically (see below). For data analysis purposes, encrypted data stripped of all PHI information will be sent to Tufts Medical center study staff via CD.

4. CMCVAMC, provide exact location where research data (original and all copies) will be stored and secured. **Paper forms will be stored in MIRECC Room B228 (informed consent, HIPAA).** 

Electronic research data will reside on several servers; the majority of the research data (regulatory documents, enrollment database) will live on the vhaphifpcmirecc server, at the following path: \\VHAPHIFPCMIRECC\Research Studies\[name] - Work Productivity. The VHAPHIHOMELESS1 server will house WebCNP Computerized Neuropsychological Testing System ; it is also stored on the Data Management Unit (DMU) at the CMC VAMC. Data stored in the Clinical database will reside on the MIRECC 1 server (\\10.36.41.70\). VINCI servers for data, applications and virtual sessions are physically located at the VA Austin Information Technology Center (AITC), located in Austin, Texas. For data analysis purposes, a copy of encrypted data stripped of all PHI information will be sent to Tufts Medical center study staff via CD.

- 5. Explain how data is to be transported or transmitted from one location to another. Encrypted and coded data via CD.
  - 5.1. Informed Consent discloses PHI transported or transmitted off-site.
  - 5.2. HIPAA Authorization discloses entities to whom PHI will be transported or transmitted. □ YES ⊠NO □N/A
    - 5.2.1. List all entities or individuals outside CMCVAMC to whom data is to be disclosed, and the justification for such disclosure and the authority. Tufts Medical Center study staff with WOC status for data analysis. Research assessment data will be housed at the Corporal Michael J Crescenz VAMC, managed by the Data Management Unit
  - 5.3. If yes, list the exact data that will be transmitted. Coded data housed at Penn(T0 randomization check list and all T1 and T2 assessment data) will be hand walked from the University of Pennsylvania to the VA. For data analysis, Research and clinical data stripped of all PHI including questionnaire responses from T0, T1, and T2, and V-WHI intervention information
  - 5.4. If yes, explain how data will be protected during transmission outside of CMCVAMC. VA to Tufts: Encrypted data stripped of all PHI on a CD sent via UPS. Penn to VA: Coded data will encrypted and hand walked from Penn to VA.
  - 5.5. Off-site, provide exact location (If off-site, attach at least one of the following.)
    - 5.5.1. Data Use/Transfer Agreement TYES NO N/A
    - 5.5.2. Off-Site Storage/Transfer of Research Data XYES NO N/A
    - 5.5.3. Memorandum of Understanding XYES NO N/A
    - 5.5.4. (Note: VA data disclosed to a non-VA investigator at an academic affiliate for research purposes needs to be approved by the Under Secretary of Health or designee.)
- 6. List who is to have access to the data and how they are to access it (anyone who has access to the data is responsible for its security). Principal Investigator (PI), investigators at Tufts, Senior Research Coordinator, Coordinator, Research Assistant, Statisticians/Data Analysts, study therapists/clinicians. VA TVHS study staff will not have access to any CMCVAMC participants' data.
- 7. Describe who is to have access and be responsible for the security of the information (e.g., the Coordinating Center, the statistician, and PI who has ultimate responsibility). **Principal**

Investigator (PI), investigators at Tufts, Senior Research Coordinator, Coordinator, Research Assistant, Statisticians/Data Analysts, study therapists/clinicians.

- 8. Provide mechanisms used to account for the information. All electronic data is stored on a user-restricted secure CMCVAMC server. All paper forms, including informed consent and HIPAA, will be stored in locked cabinets in MIRECC Room B228. Note, for several months from 12/16/2015 until 2/26/16, the DMU at the University of Pennsylvania was utilized for new and reconsented participants.
- 9. Give security measures that must be in place to protect individually identifiable information if collected or used. All electronic data is stored on a user-restricted secure CMCVAMC server. Any paper forms, including informed consent and HIPAA, will be stored in locked cabinets in MIRECC Room B228. Research staff members are trained on privacy and confidentiality.
- 10. How and to whom a suspected or confirmed loss of VA information is to be reported. CMCVAMC IRB following the CMCVAMC IRB SOP.
- Identify any circumstances that may warrant special safeguards to protect the rights and welfare of subjects who are likely to be vulnerable including, but not limited to, those subjects who may be susceptible to coercion or undue influence, and describe appropriate actions to provide such safeguards. N/A
- 12. Electronic PHI will be stored on the following:
  - 12.1. CMCVAMC desktop computer with password protection and/or encryption. □YES ⊠ NO □N/A
    - 12.1.1. If yes, identify where the desktop is located.
  - 12.2. CMCVAMC secure server. ⊠YES □NO □N/A
    - 12.2.1. If yes, identify the CMCVAMC server.: MIRECC server study folder name: \\VHAPHIFPCMIRECC\Research Studies\[name] - Work Productivity; MIRECC 1 server (10.36.41.70); VHAPHIHOMELESS1 server - DMU and CNB VhaphimulhI2 VHAPHIMULRESHL
    - 12.2.2. External drive that is password protected and/or encrypted. □YES ⊠NO □ N/A
      - 12.2.2.1. If yes, identify the external drive.
  - 12.3. Off-Site server TYES NO N/A (If off-site, attach at least one of the following.)
    - 12.3.1. Provide exact location and the name of the off-site server.
    - 12.3.2. Data Use/Transfer Agreement YES NO N/A
    - 12.3.3. Off-Site Storage/Transfer of Research Data YES NO N/A
    - 12.3.4. Memorandum of Understanding XYES NO N/A
- 13. Explain how data is to be transported or transmitted from one location to another. Encrypted data stripped of all PHI on a CD to Tufts Medical Center. Encrypted data burned onto CD will be hand walked from the University of Pennsylvania to the VA (DMU data).
- 14. Informed Consent discloses PHI transported or transmitted off-site.
- 15. HIPAA Authorization discloses entities to whom PHI will be transported or transmitted. ⊠YES □NO □N/A

- 16. List all entities or individuals outside CMCVAMC to whom data is to be disclosed, and the justification for such disclosure and the authority. Tufts statisticians and investigators in order for data analysis, who will be listed on the research study form once they have obtained WOC status.
- 17. Clarify what protection exists for a database. Secure server, password and staff restricted 17.1. Data is stored:
  - 17.1.1. With identifiers ⊠YES □NO
  - 17.1.2. Coded ⊠YES □NO
  - 17.1.3. De-Identified YES NO 17.1.4. Provide the exact list of identifie
    - .4. Provide the exact list of identifiers that will be stored. Name, address(es), SS number, DOB, dates of appointments, phone number(s)
- 18. Describe the plan for protecting research data from improper use or disclosure.
  - 18.1. The Investigator must notify the Information Security Officer, Privacy Officer, IRB, Associate Chief of Staff for Research and Research Compliance Officer within one hour of the improper use or disclosure.
- 19. Is there a plan to apply for a Certificate of Confidentiality? UYES NO N/A
  - 19.1. If yes, provide a copy of the certificate with this application or to the IRB Office as soon as received.
- 20. Record Retention:
  - 20.1. The required records, including the investigator's research records, must be retained until disposition instructions are approved by the National Archives and Records Administration and are published in VHA's Records Control Schedule (RCS 10-1). VHA Handbook 1200.05 §26.h
  - 20.2. Until a schedule for local research records is published, ALL records including identifiers must be retained." ORO/ORD Guidance on Informed Consent Form Modifications Addressing VA Record Retention Requirements (July 23, 2009)
  - 20.3. If there are additional procedures for record retention, explain further.
- Z. Qualification of the Investigators
